**03.09.2025**

## STUDY PROTOCOL

### SHORT CHAIN FATTY ACIDS PROFILES IN AMYOTROPHIC LATERAL SCLEROSIS: LONGITUDINAL EFFECTS OF DISEASE AND MEDITERRANEAN DIET INTERVENTION

**WP1 – Creation of the study design, informed consent for patients, definition of the study population and approval of the protocol**

WP1	Objectives	Status
Deliverables	Establishment of the study protocol	Completed
	Ethics Committee approval	
	Informed consent form	Completed

**WP2 - Determination of the reagents/materials needed at all stages of the research and initiation of procurement procedures**

WP 2	Objectives	Status
Deliverables	Establishing the reagents and materials needed for the research stages (list of necessary materials and equipment, with technical specifications)	Completed
	Establishing the working protocol for neurophysiological exploration	
	Commencement of procurement procedures, contact with suppliers	Completed

**WP3 - Inclusion of patients in the study, initial visit (T0), clinical evaluation, neurophysiological evaluation, collection of biological samples and SCFA analysis (SCFAGGYC-PROF)**

WP 3	Objectives	Status

Deliverables	Identification of patients with ALS (n=44) and healthy controls (similar age and gender; n=40)	Achieved
	Explaining the objectives of the study and signing the informed consent form	Completed
	Clinical and neurophysiological assessment of each ALS patient, with completion of each patient's medical record (including ALSFRS-R)	Completed
	Collection of serum samples	Completed

**WP4 - Reassessment of ALS patients after 6 months (visit T1): clinical and neurophysiological evaluation, collection of biological samples and SCFA analysis, and introduction of the diet**

WP 4	Objectives: Dissemination of research data within the grant	Status
Deliverables	Clinical and neurophysiological assessment of each ALS patient and application of the dietary questionnaire	Completed
	Collection of serum samples	Completed
	Completion of the patient's medical file	Done
	Introduction of a dietary plan	Done

**WP5 - Final reassessment of ALS patients (visit T2): clinical assessment, neurophysiological assessment, collection of biological samples and SCFA analysis**

WP 5	Objectives	Status
Deliverables	Clinical and neurophysiological assessment of each ALS patient 6 months after introduction of the diet	Achieved
	Serum sample collection	Completed
	Completion of each patient's medical file	Completed
	Neurophysiological report	Done

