### WP 7 - Statistical analysis of collected data

WP 7	Objectives: Statistical analysis of clinical, paraclinical and electrophysiological data for each ALS patient compared to the control group	Status
Deliverables	Discovery of the SCFAGGYC-PROF profile in ALS patients at T0 compared to the control group;  Discovery of the SCFAGGYC-PROF profile P-ALS in T0 and T1 evolution;  Identification of changes in the dynamics of the SCFAGGYC-PROF profile in ALS patients comparing T0 with T2.	Achieved

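### WP7 lists no analysis of the diet period (T1 to T2); its only contrast using post-diet data, T0 versus T2, also covers the six months before the study diet

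*Combined protocol and SAP*

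**What the plan says.** The study title announces "LONGITUDINAL EFFECTS OF DISEASE AND MEDITERRANEAN DIET INTERVENTION". WP3 makes T0 the initial visit. WP4 is the six-month reassessment, T1, and covers "collection of biological samples and SCFA analysis, and introduction of the diet"; its deliverables include "Introduction of a dietary plan" and "application of the dietary questionnaire". WP5 describes T2 as "Clinical and neurophysiological assessment of each ALS patient 6 months after introduction of the diet".

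WP7 states its objective as "Statistical analysis of clinical, paraclinical and electrophysiological data for each ALS patient compared to the control group". It then lists three SCFA deliverables: the profile in patients at T0 against controls; "Discovery of the SCFAGGYC-PROF profile P-ALS in T0 and T1 evolution"; and "Identification of changes in the dynamics of the SCFAGGYC-PROF profile in ALS patients comparing T0 with T2". Diet is not mentioned in WP7, and a T1 versus T2 comparison appears nowhere in the document.

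**The concern.** T1 is the last sample before the study diet and T2 the only one after it, so T1 to T2 is the interval in which a diet effect could appear. None of the three listed contrasts covers that interval alone. T0 versus T2 contains it, together with six months of change that the study diet could not have caused.

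WP7 does not call T0 versus T2 the diet effect. But it is the only listed contrast that uses post-diet data, so a reader looking for the result promised in the title will turn to it. That reader could credit the diet with change that began before T1, or miss a diet effect that runs against earlier change. No ALS group without the study diet is described, so the patients' own T0 to T1 change is the only reference for progression. WP7 does not say that it will be used as one.

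**Working it through.** **Timeline.** From WP3 to WP5: T0 is month 0; T1 is month 6, when the diet starts; T2 is 6 months later. T0 to T2 is therefore 6 + 6 = 12 months, of which 6 (50%) precede the diet.

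**What each contrast estimates.** Let d1 be the mean change from T0 to T1, d2 the disease-related change from T1 to T2, and D the effect of the study diet.

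| Contrast | Listed in WP7? | Estimates |
|---|---|---|
| ALS versus controls, T0 | yes | baseline difference, no diet data |
| T1 − T0 | yes | d1 |
| T2 − T0 | yes | d1 + d2 + D |
| T2 − T1 | no | d2 + D |
| (T2 − T1) − (T1 − T0) | no | d2 − d1 + D, which is D if d1 = d2 |

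T2 − T0 equals the diet-period change only if d1 = 0.

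**Illustration of size.** The plan states no power, SD, correlation, drift or number of completers, so it has no figure to reproduce. Assumptions: SD 1 at each visit; two-sided 5% paired t-tests; 44 completers (the number in WP3) or an assumed 30; adjacent-visit correlation ρ of 0.5 or 0.7, with T0–T2 correlation either equal to ρ or ρ² (AR(1)).

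Contrast SDs:
- T2 − T1: √(2 − 2ρ).
- T2 − T0: √(2 − 2r), where r is the T0–T2 correlation.
- Difference in changes, T2 − 2·T1 + T0: √(6 − 8ρ + 2r).

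| SD of contrast | equal 0.5 | equal 0.7 | AR(1) 0.5 | AR(1) 0.7 |
|---|---|---|---|---|
| T2 − T0 | 1.000 | 0.775 | 1.225 | 1.010 |
| T2 − T1 | 1.000 | 0.775 | 1.000 | 0.775 |
| Difference in changes | 1.732 | 1.342 | 1.581 | 1.175 |

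Rejection rates follow from the noncentral t distribution with noncentrality (mean ÷ SD) × √n and n − 1 degrees of freedom.

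*No diet effect, constant drift per six months: how often T0 versus T2 is significant.*

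| Drift (SD) | n = 44 | n = 30 |
|---|---|---|
| 0.05 | 8-13% | 7-11% |
| 0.10 | 19-39% | 14-28% |
| 0.20 | 56-92% | 41-78% |

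These are correct detections of real 12-month change; they become errors only if read as a diet result. T1 versus T2 is not immune: at drift 0.20 and n = 44 its mean is 0.20 and it is significant 25-39% of the time. The difference in changes has mean 0 here and stays at 5%.

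*Diet effect that opposes the drift (n = 44).* Take a drift of −0.25 per six months and D = +0.50. T2 − T0 has mean −0.25 − 0.25 + 0.50 = 0 and rejects 5%. T2 − T1 has mean −0.25 + 0.50 = 0.25 and rejects 37-55%. The difference in changes has mean 0.50 and rejects 46-79%. Exact cancellation is chosen to show the mechanism.

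*Recovering T1 to T2 from the two listed results.* In patients seen at all three visits the point estimate follows by subtraction. Its standard error needs the correlation between the two listed contrasts, which is 0.50-0.65 here. Treating them as independent gives a standard error 1.41-1.64 times the true one.

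*Limits of the alternatives (n = 44, no diet effect).* If drift is 0.30 and then 0.10, the difference in changes has mean −0.20 and rejects 12-20%. If values shift by 0.2 SD at T1 only, the difference in changes has mean −0.40 in absolute terms 0.40, and rejects 32-60%; T1 versus T2 rejects 25-39%; T0 versus T2 stays at 5%.

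**The case against.** The strongest reply is that nothing listed is wrong. Changes from a common baseline at T1 and T2 carry all the mean-change information in three visits, and the trial team holds the individual data from which T2 − T1 can be computed. WP7 is a short deliverables table, not a full analysis plan, and an unlisted contrast may still have been run. The harm depends on a reader attributing T0 versus T2 to the diet, which the document does not do. The larger weakness is the lack of a concurrent ALS group off the diet, and no added contrast cures that.

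Much of this stands. T0 versus T2 is valid as description. T1 versus T2 still mixes diet and progression and is also open to misreading under drift, though less often. The illustrative figures show a mechanism, not an effect in this trial. What does not stand is that the gap is harmless: the diet aim in the title has no analysis directed at it, and a published pair of T0-based results does not give a reader a confidence interval for the diet period. The reference to dynamics in the third deliverable does not fill the gap, since it names only T0 and T2. Nor does the objective line, which names only comparison with controls and no visit.

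A side point has less weight. The dietary questionnaire is listed at T1 and not at T0, and its recall period is not given, so intake between T0 and T1 is not described. This bears on how the T0 to T1 reference is read, not on whether the contrast is missing.

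**Conclusion.** The concern holds and should be fixed. That WP7 lists no T1 to T2 analysis, and that half of the T0 to T2 interval precedes the study diet, follows from the text alone with no assumption. How far T0 versus T2 could mislead depends on pre-diet drift and within-patient correlation, which the documents do not give. Under the assumptions above the possible distortion runs from slight (8-13% significant at drift 0.05, n = 44) to dominant (56-92% at drift 0.20). The remedy gives a clearer and better-aimed report; it does not identify the diet effect, which this single-arm sequence cannot separate from progression without assuming constant drift and no season or visit effect.

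**What to change.** In WP7, for each SCFA:

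1. Report T1 versus T2 with a 95% CI as the change over the diet period, and state that it still includes disease progression.
2. Report the within-patient difference in changes, (T2 − T1) − (T1 − T0), with a 95% CI as a supporting, drift-adjusted estimate. State that it equals the diet effect only if drift is constant and there is no season or visit effect.
3. Obtain both as paired contrasts in patients with the required visits, stating that they describe those patients only. Alternatively, use a repeated-measures model with visit as a three-level factor and an unstructured covariance, stating the missing-at-random assumption. A random intercept alone is not advised, because it forces the same correlation on all pairs of visits. Give the number of patients at each visit.
4. Keep T0 versus T2 as a description of total 12-month change and do not interpret it as the diet effect.
5. State that the diet effect cannot be isolated, because no concurrent ALS group without the study diet is described.
6. Label the additions post hoc, since WP7 is already marked as achieved, and present them as estimates with CIs rather than confirmatory tests.

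**Cost.** No new data: WP4 to WP6 mark the T1 and T2 samples and the assays as complete. It adds two estimates per SCFA to a plan that states no multiplicity rule. Precision is the main price. The standard error of the difference in changes is about 1.5-1.7 times that of T1 versus T2. Its 95% CI half-width is 0.36-0.53 SD with 44 completers and 0.44-0.65 SD with 30, against 0.24-0.30 and 0.29-0.37 SD for T1 versus T2. Its detectable effect at 80% power is 0.51-0.75 SD (n = 44) or 0.62-0.92 SD (n = 30), so it may well be inconclusive.

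### The supplied protocol post-dates its own analysis, so it cannot verify that the three SCFA contrasts were chosen in advance, and it omits T1-T2, the only interval wholly on the diet

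*Combined protocol and SAP*

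**What the plan says.** The document is headed as the study protocol and carries the date 03.09.2025, with no label saying whether this is a version, approval or upload date. Each work package lists deliverables beside a status column.

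- **WP1** lists "Establishment of the study protocol" as completed, and its heading mentions approval of the protocol. No date or text of that version is given.
- **WP3** covers "Identification of patients with ALS (n=44) and healthy controls (similar age and gender; n=40"), with status achieved.
- **WP4** places T1 at 6 months and introduces the diet at that visit. It is marked completed or done.
- **WP5** records the T2 visit: "Clinical and neurophysiological assessment of each ALS patient 6 months after introduction of the diet Achieved".
- **WP6** marks the SCFA assays and data entry as completed.
- **WP7** names three contrasts. The first is "Discovery of the SCFAGGYC-PROF profile in ALS patients at T0 compared to the control group". The second, within patients, is "Discovery of the SCFAGGYC-PROF profile P-ALS in T0 and T1 evolution". The third is the change over the whole study, "in ALS patients comparing T0 with T2. Achieved", where the last word is the status entry.

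WP7 names no lead analyte, test, significance level or multiplicity rule, and reports no p-value or result.

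**The concern.** A protocol normally lets a reader separate analyses chosen before the results from those chosen after. This version cannot do so, because the cell that names the contrasts also records the analysis as achieved. If the list was settled with the results in view, nominal p-values and confidence intervals would not have their stated error rates, and exploratory findings could pass for confirmatory ones.

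The list also fits the title poorly. The title announces effects of a Mediterranean diet intervention, yet the one within-patient comparison lying wholly on the diet, T1-T2, is missing. A reader looking for the diet result is left with T0-T2, which covers an equally long diet-free period as well.

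**Working it through.** The plan states no error rate, power or p-value, so there is no figure of its own to reproduce. The check has three parts.

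**1. Order of events.** WP3 to WP7 are all marked achieved, completed or done in a document dated 03.09.2025. The text as it stands therefore post-dates the analysis. WP1 shows that a protocol was established as a first step, but the supplied text does not say when, or which contrasts it held.

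**2. What the design offers.** Three patient visits and one control group make four sets of measurements, so there are 4 × 3 / 2 = 6 pairwise contrasts.

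| Contrast | Listed in WP7 | Period covered |
|---|---|---|
| T0 vs controls | yes | baseline |
| T1 vs controls | no | end of the diet-free period |
| T2 vs controls | no | after 6 months of diet |
| T0-T1 | yes | 6 months, no diet |
| T0-T2 | yes | 6 months without diet + 6 months on diet |
| T1-T2 | no | 6 months on diet |

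For patients seen at all three visits, (T2 − T0) = (T1 − T0) + (T2 − T1). Subtracting the two listed changes recovers the mean T1-T2 change in those patients. It does not give its confidence interval, which needs the within-patient covariance.

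**3. Scale.** Assumptions, none stated in the documents: no true effect, one analyte, normal data, no dropout, unadjusted two-sided 5% t-tests (two-sample against controls, paired within patients), and equal correlation between visits. From WP3: 44 patients and 40 controls. There were 40,000 simulated trials per setting.

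| Probability of at least one p < 0.05 | correlation 0.3 | 0.5 | 0.7 |
|---|---|---|---|
| One contrast fixed in advance | 0.050 | 0.049 | 0.050 |
| The three listed | 0.126 | 0.132 | 0.134 |
| Any of the six | 0.202 | 0.200 | 0.195 |

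A cross-check for three independent tests gives 1 − 0.95³ = 0.143. The simulated values are slightly lower because the contrasts share T0. A repeat with 20,000 trials and correlations from 0 to 0.8 gave 0.127 to 0.134 for the three listed.

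The two steps mean different things. From 5% to about 13% is the cost of testing three contrasts without adjustment, and it arises even with perfect pre-specification. Only the step from about 13% to about 20%, a ratio of 0.20 / 0.13 ≈ 1.5, relates to free choice among six.

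The number of analytes in the profile is not given. If m analytes were each tested in all three contrasts, independence would give 1 − 0.95^(3m): 37% for m = 3, 60% for m = 6 and 79% for m = 10. That too is multiplicity, not an effect of the date.

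**The case against.** The strongest reply is that unverifiable is not the same as absent. A late date and a filled-in status column fit a list of deliverables written at the start and ticked off later. WP1 points to an earlier protocol. The front pages were not available for this review, so version details may stand there. Two of the three contrasts follow directly from the design: T0 against controls, and T0-T1 as the diet-free interval. WP7 words two of its three contrasts as discovery, and nothing in the text claims confirmation.

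All of this stands, and it limits the point. A reader might infer that the contrasts were picked after the results were known, or that p-values from them do overstate the evidence. The documents support neither: they contain no p-value or result, and no sign that any contrast was dropped because of its outcome. The omission of T1-T2 is a weakness in the choice of contrasts, not evidence of selection. A reader might also set 20% against 5% and speak of a fourfold error rate, but that comparison counts ordinary multiplicity as if the date had caused it.

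The reply does not remove the gap. Pre-specification has to be shown from a dated text, and this version is not one that predates the data. Nor does the design alone explain the list, since it yields T1-T2 as readily as T0-T2.

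**Conclusion.** The point holds in conditional form. From this version alone, pre-specification of the three contrasts cannot be verified, and nominal p-values may overstate the evidence if the contrasts were chosen after the data. Under the assumptions above, the false-positive chance for one analyte is about 13% for the three listed contrasts and would be about 20% under free choice among six. The increase from 13% to 20% does not apply if an earlier dated version lists the same three.

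Separately, and whatever the dates, WP7 lacks the contrast that covers the on-diet interval alone. T1-T2 would still not isolate the diet from disease progression, because no patient group without the diet is described over that interval. It does at least avoid mixing in the diet-free months.

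**What to change.** 1. Cite in WP7 the date of the approved protocol that preceded the SCFA results, and call only the contrasts it lists pre-specified.
2. If no such version can be cited, add to WP7: *This version is dated after the SCFA data were analysed. All SCFA contrasts are exploratory and are reported as estimates with 95% confidence intervals; no disease or diet effect is claimed as confirmed.*
3. In either case, report all six contrasts, including T1-T2, in one table whatever their result.
4. Do not use the present version to name a lead contrast or analyte as confirmatory, since that would itself be a choice made after the data.

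The table removes selection among contrasts. It does not remove later choices of analyte, test or missing-data handling, so those should be stated beside it.

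The cost is a wording change and one fuller table from data already held, with no new patients, visits or assays. The downside is a more modest conclusion if no earlier dated version can be cited.
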